Preterm infants matching the inclusion criteria (listed elsewhere) will be enrolled in a cross-over trial of two modes of non-invasive respiratory support: nasal intermittent positive pressure ventilation (PC-NIV) and NAVA NIV (Sevo-n Neonatal Ventilator, Getinge, Solna, Sweden).

In order to compare the two modes at the same level of PIP, a 20-minute registration of ventilator parameters during assistance on NAVA-NIV will allow calculating the mean PIP (peak inspiratory pressure)..

The ventilator settings other than PIP (i.e. FiO₂, PEEP, IT, RR) will be based on the setting optimized by the attending physicians prior to the study entry.

Infants will then receive a randomized sequence of 1-hour assistance by NAVA NIV and 1-hour assistance PC-NIV at the same level of PIP or vice-versa.

FiO₂ will be adjusted in order to maintain SpO₂ 88-93% in infants ≤ 32 weeks of postconceptional age, 90-95% in infants > 32 weeks of postconceptional age.

Infants will receive respiratory support in a standardized supine position during the study period.

RANDOMIZATION

The randomization will be created by generating casual numbers by specific MatLab functions. Closed, opaque, sequentially numbered envelops will be then created by the collaborators from the department of Elettronica, Informazione e Bioingegneria – DEIB, Politecnico di Milano University. After enrolment, physicians will open the envelop containing the sequence of randomization.

ENDPOINTS

PRIMARY

Breath-by-breath variability of tidal breathing amplitude.

Tidal breathing amplitude will be recorded continuously via two, high resolution, small cameras placed inside the infant's incubator and skin (non-invasive) markers. Ventilator parameters (flow, pressure, volume and electrical diaphragmatic activity) will be recorded continuously during the study. Data will be analysed *a posteriori* applying parametric or non-parametric statistical tools depending on the results of normal distribution test and long term correlation properties will be studied by the DFA (Detrended Fluctuation Analysis) technique or similar.

SECONDARY

Breathing pattern variability (Tidal Volume, Respiratory Rate, Inspiratory Time, Duty Cycle)

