Ventilator parameters (flow, pressure, volume and the electrical diaphragmatic activity) will be recorded continuously during the study, chest and abdominal volume displacement will be detected by two high-resolution camera-based 3D depth sensors placed in the incubators. The variability of the breathing pattern will be then analyzed by the DFA technique.

Lung mechanics (lung reactance and lung resistance)

Lung mechanics will be measured by mean of the Forced Oscillation Technique (FOT) at the end of each step, by superimposing to the ventilator waveform an oscillatory pressure of small amplitude and high frequency (Fabian, Acutronic Medical Systems AG, Switzerland). Flow and pressure signals will be collected and respiratory mechanics will be evaluated by estimating offline the total respiratory system input impedance and expressed as reactance and resistance.

Gas exchange

Fraction of inspired oxygen (FiO₂), SpO₂ and transcutaneous pCO₂ will be monitored continuously.

Rate of apnoeas, desaturations, bradycardias

Episodes of apnoea, desaturation, and bradycardia will be recorded over each study period

Rate of patient-ventilator asynchronies

Patient-ventilator asynchronies will be calculated by continuous recording of ventilator parameters (flow, pressure, volume and electrical diaphragmatic activity) and by continuous recording of abdominal and chest movements by high resolution cameras placed in the incubators and skin markers on abdomen and chest

Patient's comfort

Patient's comfort will be assessed by the attending nurse at the end of each step by means of the COMFORT scale at the end of each step.

Number of caregiver interventions required

The number of interventions required by the attending personnel during each step will be also recorded: for instance interventions to improve comfort, to adjust the ventilator interface, to optimize the efficacy of respiratory support, suctioning ...

STUDY DURATION/TIME POINTS

The first part of the study will be to determine the mean PIP during NAVA NIV over a 20-minute period, followed by the cross-over, made up of two steps lasting 1 hour each. At the end of each step, a 5-minute measurement by FOT will take place. Data will be assessed at the beginning of the study (t0), every 10 minutes during the first 30 minutes and every 5 minutes during the last 30 minutes.

STATISTICAL ANALYSIS

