The sample size of the study was calculated by G-power. 25 patients are needed for a two-tailed power > 0.80 with $\alpha=0.05$, hypothesizing a normal distribution and an effect dimension of 0.59. The effect dimension was calculated considering a correlation among groups = 0.5 and tidal volume variations (used as a quantitative index for characterizing breathing amplitude variations) of newborn infants supported by nasal CPAP (0.79 ± 0.14) and after the application of nasal CPAP at 2 cmH₂O (0.71 ± 0.13) [Zannin, Pediatr Pulmonology 2018].

Measured Variables and Data Analysis

From the flow, pressure, volume and electrical diaphragmatic activity tracings, the breathing patterns will be measured (see above). The end-expiration will be identified by the two small, high resolution camera-based 3D sensors and the skin markers. FiO₂, SpO₂, tc pCO₂ will be also measured. At the end of each step lung resistance (Rrs) and reactance (Xrs) will be assessed by FOT. A dedicated

operator will record the number of episodes of apnea, bradycardia and desaturation. Patient's comfort will be assessed by the COMFORT scale. Mean (or median as appropriate) and SD (or IQR) will be calculated for all the parameters measured. Short-term variability will be determined by the variation coefficient (SD). Long-term correlation will be evaluated by the DFA technique. ANOVA or Friedman test for repeated measurements as appropriate according to data distribution will be used to verify differences in each of the parameters analysed, considering groups.

ETHICS

The present study will be conducted following the ICH/GCP International Conference of Harmonization/Good Clinical Practice rules and all the applicable regulations, including the declaration of Helsinki, June 1964, modified by the World Medical Association General Assembly in Seoul, 2008.

The study protocol has been approved by the local Ethical Committee, Comitato Etico Milano di Area 2, on March 1st 2019.

REFERENCE

- [1] K. Costeloe, E. Hennessy, A. T. Gibson, N. Marlow, A. R. Wilkinson, and for the EPICure Study Group, "The EPICure Study: Outcomes to Discharge From Hospital for Infants Born at the Threshold of Viability," *Pediatrics*, vol. 106, no. 4, pp. 659–671, 2000.
- [2] P. Y. Ancel *et al.*, "Survival and morbidity of preterm children born at 22 through 34 weeks' gestation in France in 2011: results of the EPIPAGE-2 cohort study," *JAMA Pediatr.*, vol. 169, no. 3, pp. 230–238, 2015.

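### Does leaving the analysed minutes of each 1-hour step unstated put the breathing-variability comparison at risk?

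*Combined protocol and SAP*

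**What the plan says.** Under Endpoints (Primary), "Tidal breathing amplitude will be recorded continuously via two, high resolution, small cameras", and "long term correlation properties will be studied by the DFA (Detrended Fluctuation Analysis) technique or similar". Under Measured Variables and Data Analysis, the summaries are named without a stretch of time or a number of breaths: "Short-term variability will be determined by the variation coefficient (SD). Long-term correlation will be evaluated by the DFA technique". The test is repeated-measures ANOVA or Friedman, according to distribution.

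Under Study Duration/Time Points, a 20-minute NAVA-NIV registration comes first, "followed by the cross-over, made up of two steps lasting 1 hour each". Data are assessed at the start, then "every 10 minutes during the first 30 minutes and every 5 minutes during the last 30 minutes". Read per step and leaving out the starting point, that is nine points (10, 20, 30, 35, 40, 45, 50, 55 and 60 minutes), six of them after minute 30. The same section adds: "At the end of each step, a 5-minute measurement by FOT will take place". It does not say whether those 5 minutes lie inside the hour. The forced oscillation technique (FOT) is described under Endpoints (Secondary) as "superimposing to the ventilator waveform an oscillatory pressure of small amplitude and high frequency (Fabian, Acutronic Medical Systems AG, Switzerland").

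Event counts do have a period (each study period), and FOT and COMFORT are tied to the end of each step. The variability endpoints have no such anchor.

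**The concern.** A variation coefficient or a DFA exponent needs a run of breaths, and the plan leaves that run open. The whole hour, an average over scheduled points and a late segment all comply with the text.

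Two harms could follow. First, an analyst who tried several windows and reported the most favourable would exceed the nominal 5% false-positive rate on the primary endpoint. Second, the steps follow one another with no stated adaptation interval. If variability moves gradually from the level under the previous mode, early minutes would carry part of that level and shrink the NAVA-PC difference. Randomising the order does not restore an average contrast lost in this way. If FOT falls inside the hour, minutes 55-60 would also contain breaths taken under superimposed oscillation.

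**Working it through.** **The plan's own figure.** Inputs from Statistical Analysis: 0.79 ± 0.14 and 0.71 ± 0.13, correlation 0.5, two-sided alpha 0.05.

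- SD of the difference = √(0.14² + 0.13² − 2·0.5·0.14·0.13) = 0.1353.
- Standardised effect = 0.08/0.1353 = 0.591.
- The exact paired t test gives power 0.810 at n = 25 and 0.792 at n = 24. This agrees with "25 patients are needed for a two-tailed power > 0.80", so the sample size is not in question.

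**Choosing a window by its result.** Simulation with n = 25, no true difference and a paired t test. The correlation between an infant's two half-hour differences is assumed.

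| Reported result | corr. 0.9 | corr. 0.7 | corr. 0.5 |
|---|---|---|---|
| Better of whole hour and last half | 0.061 | 0.068 | 0.075 |
| Best of first half, last half, whole | 0.072 | 0.087 | 0.099 |

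A single window gives 0.050.

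**Dilution.** Assume an exponential approach with time constant τ, every infant at the NAVA level when step 1 starts, and equal sequences. Let f be the mean of exp(−t/τ) over the window and e = exp(−60/τ). Without any reset during FOT, the share of the difference kept is 1 − f (NAVA first) and 1 − f − f(1 − e) (PC first), averaging 1 − f − 0.5f(1 − e). If FOT fully resets the infant to some other level, the average is 1 − f.

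Example, whole hour, τ = 10: f = 10(1 − exp(−6))/60 = 0.166 and e = 0.002. The shares are 0.834 and 0.668, averaging 0.751, so power is 0.568. With full reset the average is 0.834 and power 0.658.

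Power at n = 25, from no reset to full reset, with the SD held at 0.1353:

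| Window | τ = 1 min | τ = 5 | τ = 10 |
|---|---|---|---|
| Whole hour | 0.790-0.797 | 0.699-0.739 | 0.568-0.658 |
| Nine points | 0.810 | 0.789-0.796 | 0.720-0.752 |
| Minutes 30-55 | 0.810 | 0.809 | 0.788-0.795 |

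**Cost of the late window.** Minutes 30-55 would be the late segment if FOT lies inside the hour. Assume 40 breaths/min and a variation coefficient (CV) of 0.75. The window then keeps 25 × 40 = 1,000 of 2,400 breaths. With var(CV) = CV²(0.5 + CV²)/n = 0.598/n, the variance of the difference rises by 2(0.598/1,000 − 0.598/2,400) = 0.00070 if breaths are independent. The SD becomes 0.1378 and power 0.795. If the effective number of breaths is one fifth, the SD is 0.1476 and power 0.739; if one tenth, 0.1590 and 0.675. At τ = 5 dilution barely alters these figures. Simulated DFA exponents (fractional Gaussian noise, true exponents 0.6 to 0.8) have an SD of 0.033-0.040 on 2,400 breaths and 0.045-0.053 on 1,000.

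**Side by side at τ = 5.** Late window 0.795, 0.739 or 0.675; whole hour 0.699-0.739; nine points (granted whole-hour precision) 0.789-0.796. The late window beats the whole hour if breaths are independent, roughly ties at one fifth and loses at one tenth. It does not clearly beat the nine points in any of the three cases.

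**The case for a change.** The strongest case for a change is that the omission touches the primary endpoint, one sentence would close it, and fixing a window in advance helps whatever the settling time. Denser late sampling may hint at a late focus, but the text does not say so. If settling is slow, the loss is large: at τ = 20 the whole hour has power 0.328-0.492, against 0.653-0.709 for minutes 30-60 before precision loss. If the moment of switching counted as a scheduled point, the schedule would do worse than shown (ten points, τ = 5, no reset: about 0.65).

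Part of this stands. The window is unstated, so is the position of FOT relative to the hour, and the type I figures are correct for an analyst who picks by result. But those figures show what the text permits, not what is likely. The dilution argument is weaker than it looks:

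- It needs a settling time, a state at the start of step 1 and an FOT effect that the documents do not give. At τ = 20 the 20-minute run-in is only one time constant, so a start at the NAVA level is not assured.
- Shrinkage in both sequences is not general. With τ = 10 and FOT returning infants to the PC level, NAVA-first keeps 100% and PC-first 67%. With a reset below PC by the size of the NAVA-PC difference, NAVA-first is inflated to 117%.
- The model averages momentary levels. A DFA exponent is not such an average, so the dilution figures do not cover DFA.

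**Conclusion.** No change follows. The plan leaves a definition unwritten that analysts must supply in any case. The whole step, the scheduled points and a late segment are all reasonable readings, and each gives a test at the nominal level if used alike for both modes and not chosen by its result. The harm that needs no assumption about physiology, a type I error of 0.061-0.099 instead of 0.05, arises only from selective reporting; its size rests on the assumed correlation of 0.9 to 0.5 between half-hour differences.

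Requiring the last 30 minutes would be a trade-off, not a correction. It protects against slow drift but discards more than half the breaths, and at τ = 5 its power (0.675-0.795) straddles that of the whole hour (0.70-0.74). Which is better turns on the time constant, breath rate, variation coefficient and correlation between breaths, all of them assumed here. Dilution remains a conditional possibility for the variation coefficient only, and its size may differ by sequence. The planned sample size is reproduced and unaffected.

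### The plan names ANOVA or Friedman without saying how repeated readings become a NAVA-NIV versus PC-NIV comparison; Friedman then either may not isolate the mode effect or is a low-powered sign test

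*Combined protocol and SAP*

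**What the plan says.** Under STUDY DURATION/TIME POINTS the cross-over has two one-hour steps after a 20-minute NAVA-NIV recording. The reading schedule is given once: "Data will be assessed at the beginning of the study (t0"), then "every 10 minutes during the first 30 minutes and every 5 minutes during the last 30 minutes". It is not expressly assigned to each step, but it covers exactly one hour, so per-step use is the natural reading.

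Under STATISTICAL ANALYSIS, Measured Variables and Data Analysis, the only testing rule is "ANOVA or Friedman test for repeated measurements as appropriate according to data distribution will be used to verify differences". The sentence applies to every parameter and ends by saying that groups are taken into account. It does not define groups, name the factors (mode, time, period), give t0 a role, or say whether readings are first reduced to one value per infant per mode.

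The sample-size paragraph assumes a simple paired comparison: "25 patients are needed for a two-tailed power > 0.80 with" a 5% significance level, "hypothesizing a normal distribution and an effect dimension of 0.59". It adds: "The effect dimension was calculated considering a correlation among groups = 0.5".

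**The concern.** A parameter read repeatedly in both modes, such as gas exchange, has two crossed within-infant factors: mode and time. Friedman accommodates one. The plan lets the data distribution choose between ANOVA and Friedman, so a non-normal parameter goes to a test that cannot hold mode and time together. A mode-by-time repeated-measures ANOVA could do so, but it has no counterpart in the Friedman branch.

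Two things are at stake. If the readings enter Friedman directly, a small p-value may reflect change over the hour, or the t0 reading, and be reported as a mode difference. If they are first reduced to one value per mode, Friedman is a sign test, and the power the trial was sized for is not available. The second point could also reach the primary endpoint, if its variability index is one value per step and is judged non-normal.

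**Working it through.** **1. The plan's own figure.** Inputs from the sample-size paragraph: 0.79 ± 0.14, 0.71 ± 0.13, correlation 0.5.

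- SD of the difference = √(0.14² + 0.13² − 2 × 0.5 × 0.14 × 0.13) = √0.0183 = 0.1353.
- Effect = 0.08 / 0.1353 = 0.591, matching the stated 0.59.
- Two-sided paired t-test at 0.05 (noncentral t): power 0.792 at N = 24 and 0.810 at N = 25.

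So 25 reproduces, as a single paired comparison of two conditions.

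**2. Readings.** The first 30 minutes give 3 (10, 20, 30) and the last 30 give 6 (35 to 60), so 9 per step. Two steps give 18, and a single t0 makes 19. Pairing by time point gives 25 × 9 = 225 infant-by-time pairs.

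**3. Three ways to run Friedman.** Simulation with 25 infants and no mode effect. Assumed, because the documents give none of these: reading SD 1, infant SD 1, infant-by-mode SD 0.5 to 1, exponential autocorrelation with time constant 5 to 20 minutes. Drift is linear within each step and identical in both modes.

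| Analysis | No drift | Drift 0.5 SD | Drift 1 SD |
|---|---|---|---|
| (a) Friedman over 18 readings | 0.07–0.14 | 0.29–0.41 | 0.89–0.96 |
| (b) Friedman, 225 infant-by-time blocks | 0.20–0.39 | drift cancels within each pair | drift cancels within each pair |
| Paired t-test on step means | 0.04–0.06 | 0.04–0.06 | 0.04–0.06 |

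For (b), even with no infant-by-mode variation, autocorrelation alone gives 0.10 to 0.28.

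Sensitivity of (a):

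- Ramping the drift from minute 0, so that less of it falls between the first and last readings, gives 0.22 to 0.30 at 0.5 SD and 0.73 to 0.85 at 1 SD.
- With total variance 1, half of it between infants, and serial correlation 0 or 0.8 per 5 minutes, the rates are 0.19 to 0.26 at 0.25 SD, 0.75 to 0.76 at 0.5 SD and 1.00 at 1 SD.
- Under those same assumptions, adding t0 as a 19th column with no drift gives 0.39 for a t0 shift of 0.5 SD and 0.97 to 0.99 for 1 SD.

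**(c) Friedman on one summary per mode.** With two columns the statistic is (2s − 25)²/25, where s is the number of infants with the higher value on NAVA-NIV. It exceeds 3.841 only if |2s − 25| > 9.80, that is s ≥ 18 or s ≤ 7. This is the sign test.

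- Exact size at N = 25: 0.043.
- Chance that one infant's difference has the expected sign: Φ(0.591) = 0.723.
- Power = P(s ≥ 18) + P(s ≤ 7) for a binomial (25, 0.723) = 0.613.
- About 40 infants are needed for 80% (0.805 at N = 40).
- Wilcoxon signed-rank at N = 25: about 0.78.

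**The case against.** The testing sentence does end with a reference to groups. The sample-size paragraph uses that word for the two paired conditions, and the primary objective is NAVA-NIV compared with PC-NIV. A comparison by mode is therefore pointed to, if loosely. No section says that all readings enter one omnibus test, that infant-by-time pairs serve as blocks, or that t0 is a condition. A mode-by-time ANOVA, or a test on per-mode summaries, fits the text equally well and is not misled by drift common to both steps. Randomised order also balances change between periods: with a period effect of 0.25 to 1 SD ignored, the paired contrast rejected in 3.2% down to 0.2% of null trials, which costs power and does not create false positives.

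All of this stands. A reader might infer that the trial's error rate is not 5%, that a significant gas-exchange result would be no evidence of a mode difference, or that only a two-factor ANOVA can test mode. The documents support none of these. A paired test on summaries tests mode, and so does Friedman on summaries.

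The scope is also limited. FOT and COMFORT are taken at the end of each step, event rates and caregiver interventions are recorded per period or step, and the primary endpoint may be one index per step. The inflated rates concern only parameters analysed through their repeated readings.

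What the objection does not remove is the Friedman branch itself. Naming the groups does not say how 18 readings become a mode test: analysis (b) also compares by group, and it rejects too often without any drift.

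**Conclusion.** The point holds as an under-specified analysis with a weak non-parametric branch, not as a demonstrated wrong test. For repeatedly read parameters, each way of running the stated Friedman test has a fault: across all readings it does not isolate mode; on infant-by-time blocks it is anticonservative (about 0.20 to 0.39 under the assumed variance components); on per-mode summaries it is valid but gives about 61% power against the planned figure above 80%.

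The simulated rates rest on assumed drift, autocorrelation and variance split, and on the schedule applying to each step. They differ considerably between assumption sets (0.22 to 0.76 at 0.5 SD drift), so they show direction and not a forecast. The 61% rests on the plan's effect of 0.59 and normally distributed differences; under clear non-normality, where this branch would be used, the gap to other tests would differ. Applying 0.59 to parameters other than the one the trial was sized on is also an assumption. The change should be made before the data are analysed.

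**What to change.** Replace the testing sentence with:

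> For each repeatedly read parameter, readings in a prespecified window of each step are reduced to one value per infant per mode; t0 is described but not tested. NAVA-NIV and PC-NIV are compared by the within-infant difference, with a paired t-test, or Wilcoxon signed-rank if the differences are clearly non-normal.

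This matches the comparison the sample size was built on (81% power at 25 infants) and avoids the sign test as fallback. If the time course is of interest, add a linear mixed model with mode, period, time and mode × time, and random infant and infant-by-mode effects, and draw the conclusion from the mode contrast.

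The cost is a few sentences of analysis text and no new data. There is no omnibus test over time points, and the averaging window must be fixed in advance, including whether the minutes just after the change of mode count.

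### With two modes and one value per infant per mode, the Friedman fallback is the sign test; the Wilcoxon signed-rank test would usually recover about 0.01 to 0.06 of overall power

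*Combined protocol and SAP*

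**What the plan says.** Under Study Intervention, each infant receives both modes: "Infants will then receive a randomized sequence of 1-hour assistance by NAVA NIV and 1-hour assistance PC-NIV", or the reverse order. The primary endpoint text makes the choice of test depend on the data, "applying parametric or non-parametric statistical tools depending on the results of normal distribution test". The Statistical Analysis section names ANOVA and one alternative to it: "Friedman test for repeated measurements as appropriate according to data distribution will be used to verify differences in each of the parameters analysed, considering groups". No other non-parametric comparison appears. The plan does not say which normality test is used, at what level, or whether it is applied to the within-infant differences or to each mode.

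The sample size is a paired calculation made under normality. It states that "25 patients are needed for a two-tailed power > 0.80" at a two-sided 0.05 level, "hypothesizing a normal distribution and an effect dimension of 0.59", and "The effect dimension was calculated considering a correlation among groups = 0.5". No power is given for the non-parametric branch.

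Two of the secondary measurements supply one value per step by design: "At the end of each step, a 5-minute measurement by FOT will take place", and "comfort will be assessed by the attending nurse at the end of each step by means of the COMFORT scale".

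**The concern.** Friedman is designed for three or more related conditions. With two, ranking within an infant leaves only a 1 and a 2, so the size of each difference is discarded. The signed-rank test also drops the normality assumption but keeps the ordering of the differences by size.

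The fallback covers the primary endpoint and every secondary parameter. At 25 infants the power is only just above 0.80 even under the parametric assumptions, so there is little margin to lose.

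**Working it through.** **Inputs from the sample-size paragraph.** Means and SDs 0.79 ± 0.14 and 0.71 ± 0.13, correlation 0.5, n = 25, two-sided α = 0.05.

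**1. The plan's own figure.** SD of the difference = √(0.14² + 0.13² − 2 × 0.5 × 0.14 × 0.13) = √0.0183 = 0.1353. Standardised paired effect = 0.08 / 0.1353 = 0.591, as stated. The noncentral t distribution gives a paired t power (equivalent to ANOVA with two conditions) of 0.810. With the rounded 0.59 it is 0.808 at n = 25 and 0.790 at n = 24. The stated 25 is reproduced.

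**2. Friedman with two conditions.** If S of n infants are higher on one mode, the statistic is Q = (2S − n)²/n. At n = 25, S = 17 gives 9²/25 = 3.24 (not significant) and S = 18 gives 11²/25 = 4.84 (above 3.84). This is the rejection region of the exact two-sided sign test, with size 0.043.

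**3. Benchmark with normal differences.** P(difference > 0) = Φ(0.591) = 0.723. Power is 0.61 for Friedman, 0.79 for signed-rank (exact critical value W ≤ 89, size 0.048) and 0.81 for paired t. This is not the loss in the planned procedure, because data that pass the normality test go to ANOVA.

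**4. The whole two-stage procedure.** Assumptions: Shapiro-Wilk at 0.05; if it fails, Friedman or signed-rank; otherwise paired t. The three margins keep the plan's means, SDs and correlation. There were 12,000 trials per scenario (simulation SE at most 0.005).

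| Normality tested on | Margins | Fallback entered | Friedman | Signed-rank |
|---|---|---|---|---|
| Differences | Normal | 5% | 0.80 | 0.81 |
| Differences | Lognormal | 7% | 0.80 | 0.81 |
| Differences | Gamma, skewness 1.4 | 22% | 0.83 | 0.84 |
| Either mode | Normal | 10% | 0.79 | 0.81 |
| Either mode | Lognormal | 26% | 0.77 | 0.81 |
| Either mode | Gamma, skewness 1.4 | 85% | 0.79 | 0.85 |

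**5. Other shapes of the differences** (unit SD, mean shift 0.591, normality tested on differences), Friedman vs signed-rank:

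- t with 5 df: 0.84 vs 0.85
- Laplace: 0.86 vs 0.86
- Uniform: 0.67 vs 0.79
- Left-skewed exponential: 0.89 vs 0.86
- Right-skewed exponential: 0.38 vs 0.79

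The last gap is partly a change of target rather than efficiency: at that mean the median shift is only 0.28 SD. Holding the median shift at 0.591 SD instead, both tests reach about 1.00 for the right-skewed shape, and Friedman is better for the left-skewed one (0.61 vs 0.51).

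**6. Size of the Friedman rule by final n.** With the chi-square cut-off, size is 0.064 at n = 24, 0.043 at n = 25 and 0.076 at n = 26. The exact sign test at n = 24 has size 0.023 and power 0.486.

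**7. The price of signed-rank.** It assumes roughly symmetric differences. For gamma differences with a zero median (40,000 trials), size is:

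| Skewness | Signed-rank alone | Two-stage, signed-rank | Two-stage, Friedman |
|---|---|---|---|
| 0.5 | 0.052 | 0.061 | 0.065 |
| 1.0 | 0.064 | 0.086 | 0.091 |
| 1.4 | 0.080 | 0.106 | 0.101 |
| 2.0 | 0.120 | 0.129 | 0.075 |

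The sign test alone has size of about 0.044 throughout. The two-stage columns assume that normality is tested on the differences.

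**The case against.** **The two-condition premise is inferred.** The time-points section schedules several assessments within each step, and nothing says that each step is reduced to one value for the primary endpoint. With more conditions, Friedman is not the sign test and the figures above do not apply. That is true, and the finding is conditional on it. But the analysis sentence makes mode the factor, the sample size is a two-condition paired contrast, and ranking across time points would mix time with mode.

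**The gain is small and rests on assumptions.** If normality is tested on the differences, the natural choice for a paired test, about 0.01 is at stake. The upper figure of 0.06 needs testing by mode and gamma margins. No document gives a distribution, and for some shapes Friedman does as well or better. All of this stands and is why the point is minor.

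**Signed-rank is weakest where it would be used.** The fallback is entered when normality fails, often because of skew, and step 7 shows its size rising. This stands for skewed differences with a zero median. It carries less weight for a null of no mode effect at all: if the two modes' values are then exchangeable within an infant, the differences are symmetric even when the margins are skewed, and the two-stage size with signed-rank is about 0.05.

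**Other gaps remain.** The change does not address period effects or the unspecified normality pre-test, and those are separate matters. The uneven size in step 6 applies only if the chi-square approximation is used, which the plan does not state.

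**Conclusion.** The concern holds as a minor point of efficiency. The equivalence with the sign test is algebra, given one value per infant per mode. For the planned procedure as a whole, a signed-rank fallback adds about 0.01 of power with normality tested on differences and 0.02 to 0.06 with normality tested on either mode, for the normal, lognormal and gamma margins examined. Under the second reading, the Friedman fallback takes overall power below 0.80 in all three.

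The size of the gain rests on the assumed margins, the Shapiro-Wilk test at 0.05 and the plan's own effect size. Its sign is not guaranteed for every shape of the differences.

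**What to change.** In the data-analysis paragraph of the Statistical Analysis section, for the two-mode comparison of continuous parameters:

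- Replace Friedman with the Wilcoxon signed-rank test on one within-infant difference (NAVA-NIV minus PC-NIV) per infant, with each step first reduced to a single value by a stated rule.
- Report the Hodges-Lehmann estimate with its 95% CI.
- State that the power above 0.80 refers to the paired parametric analysis.
- The sign test may be kept for the ordinal COMFORT score, with an exact binomial p-value.

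The cost is one or two sentences and no new data. The one-value rule also settles how the repeated assessments within a step enter the test. The downside to accept knowingly is the symmetry assumption. Against a zero-median null, the two-stage size with signed-rank is slightly better than with Friedman up to skewness 1.0 in the differences and worse from 1.4 upwards.

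### Cheap improvement: the planned cross-over analysis names no period term and the balancing of the two sequences is not described, which leaves a small, avoidable risk to power

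*Combined protocol and SAP*

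**What the plan says.** The combined protocol and SAP (STUDY INTERVENTION) sets out a two-period cross-over: "Infants will then receive a randomized sequence of 1-hour assistance by NAVA NIV and 1-hour assistance PC-NIV", or the reverse order. On allocation, the RANDOMIZATION section says "The randomization will be created by generating casual numbers by specific MatLab functions" and then describes sealed envelopes. It gives no ratio, block size or other restriction.

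Under STUDY DURATION/TIME POINTS, the run-in is "followed by the cross-over, made up of two steps lasting 1 hour each", and "At the end of each step, a 5-minute measurement by FOT will take place".

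Under STATISTICAL ANALYSIS, 25 infants are required, "hypothesizing a normal distribution and an effect dimension of 0.59". The planned comparison is "ANOVA or Friedman test for repeated measurements as appropriate according to data distribution", which "will be used to verify differences in each of the parameters analysed, considering groups". Groups is not defined. The sample-size paragraph uses the same word for two paired conditions when it gives a correlation of 0.5, so the natural reading is the two modes. No period or sequence term appears anywhere in the document.

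**The concern.** Each infant contributes a NAVA-minus-PC difference. Write T for the mode effect and π for the period difference (second hour minus first). An infant who gets NAVA first shows T − π, and one who gets PC first shows T + π. If the model contains only mode, π has two effects:

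- It adds scatter to the differences, which costs power on average over sequence splits.
- When the split is unequal, it shifts the estimated mode effect by π times (PC-first minus NAVA-first infants)/25.

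Some period difference is possible on the plan's own schedule, because the second hour comes later and follows the first step's FOT measurement. The design randomises order, but the analysis as written makes no use of it. The same sentence governs every parameter analysed, so the secondary endpoints are affected in the same way.

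**Working it through.** **Inputs** (STATISTICAL ANALYSIS): 0.79 ± 0.14 and 0.71 ± 0.13, correlation 0.5, n = 25, two-sided α = 0.05. The period difference π is an assumption: 0, 0.02, 0.04 or 0.08. One summary value per mode per infant is also assumed. The time-point text (readings "every 10 minutes during the first 30 minutes and every 5 minutes during the last 30 minutes") does not settle that.

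**1. The plan's own figure.**
SD of differences = √(0.14² + 0.13² − 2 × 0.5 × 0.14 × 0.13) = √0.0183 = 0.1353.
Effect size = 0.08 / 0.1353 = 0.591, matching the stated 0.59.
Paired t-test power is 0.810 at n = 25 and 0.792 at n = 24. So 25 reproduces exactly and is the smallest n above 0.80.

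**2. Without a period term.** On a simple (unrestricted) list the differences have variance of about 0.0183 + π². The effective effect size is then 0.08/√0.0187 = 0.585 at π = 0.02, 0.08/√0.0199 = 0.567 at 0.04 and 0.08/√0.0247 = 0.509 at 0.08. Simulated power:

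| π | simple list | 13:12, averaged over direction |
|---|---|---|
| 0 | 0.81 | 0.81 |
| 0.02 | 0.80 | 0.80 |
| 0.04 | 0.78 | 0.78 |
| 0.08 | 0.685 | 0.705 |

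On a simple list, restoring 80% average power without the term would take about 27 infants at π = 0.04 and about 33 at π = 0.08.

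**3. With a period term.** The estimate is the mean of the two sequence means. Its SE is 0.1353 × √[(1/n₁ + 1/n₂)/4], on 23 df, and power does not depend on π.
- 13:12: SE = 0.0271, noncentrality 0.08/0.0271 = 2.95, power 0.808.
- 14:11: 0.803. 15:10: 0.792.
- 17:8: SE = 0.0290, noncentrality 2.76, power 0.752.
- Averaged over Binomial(25, 0.5) splits: 0.791.

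On a simple list the break-even is near π = 0.03, where power is 0.791 both without the term and, on average, with it.

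**4. Type I error.** Averaged over a simple list, the unadjusted test rejects 5.0% at every π examined. Conditional on the split, at π = 0.08:

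| split | shift in estimate | type I error | power, by direction |
|---|---|---|---|
| 13:12 | 1/25 × 0.08 = 0.003 | 2.4% | 0.74 / 0.67 |
| 15:10 | 5/25 × 0.08 = 0.016 | 4.7% | 0.87 / 0.50 |
| 17:8 | 9/25 × 0.08 = 0.029 | 11% | 0.94 / 0.33 |

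At π = 0.04 the type I error over the same splits is 4.2%, 5.0% and 6.9%. A simple list gives 17:8 or worse with probability 0.108.

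**The case against.** **The period effect is assumed, and the large figures need it to be large.** This stands. The documents do not allow π to be sized. Power near 0.69 needs a period difference equal to the whole planned mode effect. The 11% error rate and the power of 0.33 need a 17:8 split as well.

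**The analysis is valid without the term.** Averaged over randomisation it is. A reader might infer from the conditional figures that the planned test inflates type I error. The documents do not support that: the average is 5%, and near balance the test is conservative.

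**The list may already be balanced, and groups may be meant more broadly.** Both are possible. A reader might infer that the list is simple, but the text only fails to describe balancing, and MatLab random numbers do not exclude a restricted list. Likewise, reading groups as mode is an inference, though a well-supported one.

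**The period term can cost power.** On a simple list with no period effect, average power falls from 0.81 to 0.79, below the target. This is why the term should not be adopted without balancing.

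**The 20-minute NAVA run-in looks like a reason to expect a period effect.** It is not. With carry-over cN and cP from the preceding mode, NAVA-minus-PC is T in NAVA-first infants and T + (cP − cN) in PC-first infants. That shifts the mean by (cP − cN)/2 even with equal sequences. This is carry-over, which a period term does not remove, so it is a separate question.

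**Friedman has no period term either, so a reader might want it replaced by a rank-sum test on period differences.** That is not recommended. The rank-sum test aims at a different quantity when differences are skewed, and it can lose power in that setting.

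**Conclusion.** The point holds as a cheap improvement, not as an error that undermines the trial. No period term is named and balancing is not described. For assumed period differences of 0.02 to 0.04 the loss is about 1 to 3 points of average power, and it exceeds 10 points only if the period difference is as large as the mode effect. The loss matters because the sample size leaves only one point of slack above 0.80. These figures rest on normal differences, one value per mode per infant, the plan's own SD and correlation, and no carry-over.

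**What to change.** Make both changes together:

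1. In the parametric analysis, state that mode and period are fixed effects and infant is random. With complete data and one value per mode this equals a two-sample t-test, by sequence, on the within-infant period differences. Say in the same sentence what groups means.
2. State how the two sequences are balanced. If the list is not already restricted and enrolment has not begun, generate it in permuted blocks of varying size. Sizes 2 and 4 always give 13:12 at n = 25. Sizes 4 and 6 give 14:11 at worst.

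The cost is a few lines of SAP wording and, at most, a new list. With no period effect, power moves from 0.810 to 0.808 at 13:12. If the list is already fixed and simple, the period term averages 0.79 and gains only above a period difference of about 0.03, so the choice should then be made and recorded before the data are seen. The Friedman branch can stay as planned.
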